7.8. Efficacy analysis

The efficacy of the Phase 1 patients will be presented in the subject listing only. For Phase 2a patients, efficacy will be summarized and analyzed for the FL patients in Cohort 1 and 2 and the PTCL patients in Cohort 5 only. For FL subjects in Cohort 1 and 2, efficacy will be summarized by number of prior regimens (≤ 3 vs ≥ 4). Efficacy of PTCL will be summarized by pathology subgroup as defined in Appendix B (AITL/TFH vs NOS vs Others). The efficacy listing will be provided for non-FL/non-PTCL patients in Cohort 1, 3, 4, and 6.

All efficacy analyses will be based on the efficacy analysis population. The efficacy analyses will also be analyzed in the corresponding safety analysis population in Phase 2a Cohort 1, 2, and 5 as sensitivity analyses.

7.8.1. Primary Efficacy Endpoint

Overall response rate (ORR) is defined as the proportion of subjects who achieve partial response (PR) or better as the best overall response (BOR) per Lugano criteria (Cheson, 2014, see appendix C) as assessed by the investigator. BOR is defined as the best response from treatment start to the data cutoff date (inclusive), disease progression (inclusive), or the start of new anti-cancer therapies (inclusive), whichever occurs first.

ORR will be calculated by cohort, and the associated 95% exact confidence interval (CI) will be estimated using the Clopper-Pearson method.

The primary endpoint of ORR may also be analyzed in additional subgroups of the efficacy analysis population as sensitivity analysis.

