## **8.0 ASSESSMENT OF EFFICACY**

### **8.1. Response Criteria**

Response in NHL patients will be evaluated using The Lugano Classification [4]; in CLL patients using the Workshop on Chronic Lymphocytic Leukemia (IWCLL) Guidelines for the Diagnosis and Treatment of Chronic Lymphocytic Leukemia [2]; in leukemic forms of PTCL (ATLL, PLL, LGL) using disease appropriate response criteria [77]; and in CTCL patients using the modified Severity Weighted Assessment Tool (mSWAT) and other measures as appropriate [5]. [Appendix 4](#) provides definitions and detailed descriptions of response criteria as well as guidance on selection of lesions for evaluation. Redacted copies of radiology reports will be sent to the Sponsor for review.

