7.8.2. Secondary Efficacy Endpoint

7.8.2.1. Progression free survival

Progression-free survival (PFS) is defined as the time from the start of study treatment to the first documentation of disease progression as assessed by investigator (see appendix C) or death from any cause, whichever occurs first.

Progression-free survival = (first documentation of disease progression or death – first dose date of study treatment + 1) /30.4375 in months.

PFS will be right censored for subjects who meet one of the following conditions: 1) no baseline disease assessments; 2) starting a new anti-cancer therapy before documented disease progression or death; 3) progression or death immediately after more than 6 months since the last disease assessment (or more than 12 months if beyond cycle 12); and alive without documented disease progression. The censoring convention follows the FDA guidance for Industry Clinical Trial Endpoints for the Approval of Cancer Drugs and Biologics (2018) and references within the guidance document. The censoring rules are summarized in Table 1.

Table 1. Date of Event or Censoring for PFS

Scenario	Date of PFS Event or Censoring	Outcome
Death or progression between the planned disease assessments	Date of death or first disease assessment showing PD, whichever occurs first	Event
Death before the first disease assessment	Date of death	Event
No baseline disease assessment	Date of first dose of study treatment	Censored
New anti-cancer treatment started	Date of last disease assessment prior to or on the date of new anti-cancer treatment	Censored
Death or progression immediately after missing more than 1 scheduled disease assessment ^[1]	Date of the last disease assessment before death or progression	Censored
Alive without documented disease progression	Date of last disease assessment	Censored

^[1] missing ≥ 6 months if in Cycle 1~12 or missing ≥ 12 months if beyond Cycle 12

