7.8.2.2. Duration of response

For responders (PR or better), duration of response (DOR) is defined as the time from the date of the earliest PR or better to the first documentation of disease progression or death from any cause, whichever occurs first. The censoring convention and analysis method of DOR will be the same as those for PFS in Section 7.8.2.1. DOR will be analyzed for subjects who achieved PR or better (i.e. responders only).

DOR = (first documentation of progression or death – the date of the earliest PR or better + 1) /30.4375 in months.

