7.8.2.4. Clinical benefit rate

Clinical benefit rate (CBR) is defined as the proportion of subjects who achieve stable disease (SD) or better as the best overall response (BOR) per Lugano criteria (Cheson, 2014) as assessed by the investigator. The summary and analysis method of CBR will be the same as those for ORR as described in Section 7.8.1.

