
Complete
 
Lymph nodes and extralymphatic sites
 
Nonmeasured lesion
 
Organ enlargement
 
New lesions
 
Bone marrow
	
Complete metabolic response
 
Score 1, 2, or 3^a with or without a residual mass on 5PS^b
 
It is recognized that in Waldeyer’s ring or extranodal sites with high physiologic uptake or with activation within spleen or marrow (e.g., with chemotherapy or myeloid colony-stimulating factors), uptake may be greater than normal mediastinum and/or liver. In this circumstance, complete metabolic response may be inferred if uptake at sites of initial involvement is no greater than surrounding normal tissue even if the tissue has high physiologic uptake.
 
Not applicable
 
Not applicable
 
None
 
No evidence of FDG-avid disease in marrow
	
Complete radiologic response (all of the following):
 
Target nodes/nodal masses must regress to < 1.5 cm in LDi No extralymphatic sites of disease.
 
Absent
 
Regress to normal
 
None
 
Normal by morphology; if indeterminate, IHC negative

Partial
 
Lymph nodes and extralymphatic sites
	
Partial metabolic response
 
Score 4 or 5^b with reduced uptake compared with baseline and residual mass(es) of any size:
 
At interim, these findings suggest responding disease.
 
At end of treatment, these findings indicate residual disease.
	
Partial remission (all of the following):
 
> 50% decrease in SPD of up to 6 target measurable nodes and extranodal sites.
 
When a lesion is too small to measure on CT, assign 5 mm × 5 mm as the default value.
 
When no longer visible, 0 × 0 mm.
 
For a node > 5 mm × 5 mm, but smaller than normal, use actual measurement for calculation.

Nonmeasured lesions
 
Organ enlargement
 
New lesions
 
Bone marrow
	
Not applicable
 
Not applicable
 
None
 
Residual uptake higher than uptake in normal marrow but reduced compared with baseline (diffuse uptake compatible with reactive changes from chemotherapy allowed). If there are persistent focal changes in the marrow in the context of a nodal response, consideration should be given to further evaluation with MRI or biopsy or an interval scan.
	
Absent/normal, regressed, but no increase.
 
Spleen must have regressed by > 50% in length beyond normal.
 
None
 
Not applicable

Response and Site	PET-CT–Based Response	CT-Based Response

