No response or stable disease Target nodes/nodal masses, extranodal lesions Nonmeasured lesions Organ enlargement New lesions Bone marrow	No metabolic response Score 4 or 5 with no significant change in FDG uptake from baseline at interim or end of treatment Not applicable Not applicable None No change from baseline	Stable disease < 50% decrease from baseline in SPD of up to 6 dominant, measurable nodes and extranodal sites; no criteria for progressive disease are met No increase consistent with progression No increase consistent with progression None Not applicable
Progressive disease Individual target nodes/nodal masses Extranodal lesions Nonmeasured lesions	Progressive metabolic disease Score 4 or 5 with an increase in intensity of uptake from baseline and/or New FDG-avid foci consistent with lymphoma at interim or end-of-treatment assessment None	Progressive disease requires at least 1 of the following PPD progression: An individual node/lesion must be abnormal with: LDi > 1.5 cm, and Increase by > 50% from PPD nadir and an increase in LDi or SDi from nadir 0.5 cm for lesions < 2 cm 1.0 cm for lesions > 2 cm In the setting of splenomegaly, the splenic length must increase by > 50% of the extent of its prior increase beyond baseline (e.g., a 15-cm spleen must increase to > 16 cm). If no prior splenomegaly, must increase by at least 2 cm from baseline New or recurrent splenomegaly New or clear progression of preexisting nonmeasured lesions
New lesions	New FDG-avid foci consistent with lymphoma rather than another etiology (e.g., infection, inflammation). If uncertain regarding etiology of new lesions, biopsy or interval scan may be considered.	Regrowth of previously resolved lesions A new node > 15 cm in any axis A new extranodal site > 1.0 cm in any axis; if < 1.0 cm in any axis, its presence must be unequivocal and must be attributable to lymphoma Assessable disease of any size unequivocally attributable to lymphoma New or recurrent lymphoma

5PS = 5-point scale; CT = Computed tomography; FDG = Fluorodeoxyglucose; GI = Gastrointestinal; IHC = Immunohistochemistry; LDi = Longest transverse diameter of a lesion; MRI = Magnetic resonance imaging; PET = Positron emission tomography; PPD = Cross product of the LDi and perpendicular diameter; SDi = Shortest axis perpendicular to the LDi; SPD = Sum of the product of the perpendicular diameters for multiple lesion

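### The SAP applies Lugano criteria to every Cohort 5 patient, although the protocol gives ATLL and LGL their own response criteria, and SAP section 8 does not declare the change

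*SAP*

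**What the plan says.** **SAP.** Section 7.8.1 defines the primary endpoint as the proportion "who achieve partial response (PR) or better as the best overall response (BOR) per Lugano criteria", assessed by the investigator and calculated by cohort. Section 7.8.2.4 defines clinical benefit as the proportion "who achieve stable disease (SD) or better as the best overall response (BOR) per Lugano criteria". Section 7.8.2.1 dates PFS from the "first documentation of disease progression as assessed by investigator (see appendix C"), and Appendix C reproduces only protocol Table A4-11, the Lugano table. Section 7.8.2.2 names no progression criteria for DOR: "The censoring convention and analysis method of DOR will be the same as those for PFS in Section 7.8.2.1". Cohort 5 is one of the three cohorts with aggregated efficacy (SAP 7.8). Appendix B puts ATLL, T-cell prolymphocytic leukemia and LGL in its *Others* subgroup.

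**Protocol.** Section 8.1 uses Lugano for NHL but evaluates response "in leukemic forms of PTCL (ATLL, PLL, LGL) using disease appropriate response criteria". Appendix 4, section 8, gives Table A4-12 for ATLL and Table A4-13 for LGL, and encourages investigators to use IWCLL for PLL. The Appendix 1 schedule has a separate row for response assessment in leukemic subtypes.

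**Declared changes.** SAP section 8 names three: aggregated efficacy limited to FL and PTCL, lymph node response replaced by dominant mass response, and mixed CTCAE versions. Response criteria are not among them.

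**The concern.** Read literally, the SAP replaces the protocol's disease-specific criteria for ATLL and LGL with Lugano, on the primary endpoint, without saying so. A reader of the Cohort 5 or *Others* ORR could not tell which criteria produced it.

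The protocol sets no success criterion, so the reported rate and its exact interval are the main product of this cohort. One rule does use response counts: Protocol 11.2.2 and SAP 5.2 close a cohort with fewer than 2 responses in its first 20 patients. The AITL/TFH and NOS columns are not affected.

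**Working it through.** **1. Do the criteria differ in substance?**

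- *ATLL, partial response.* Table A4-12 requires decreases of at least 50% in blood and in skin, as well as in nodes and extranodal masses, lasting at least 4 weeks. The CT column of SAP Appendix C requires a "decrease in SPD of up to 6 target measurable nodes and extranodal sites" of more than 50%. It has no blood item, and the SAP definition of best overall response has no persistence rule. A patient can therefore be a Lugano PR but not an ATLL PR. The 4-week mark also applies to stable disease, so clinical benefit rate is touched too.
- *Spleen.* With splenomegaly at baseline, CT-based PR needs more than 50% regression of the excess length. Table A4-12 asks only for no increase. Here the difference runs the other way.
- *ATLL, progression.* In Table A4-12, a rise in flower cells of at least 50% from nadir with an absolute lymphocyte count above 4 x 10^9/L is progression. Appendix C has no explicit blood item. The SAP does not say whether "Assessable disease of any size unequivocally attributable to lymphoma" would cover it.
- *LGL.* Table A4-13 rests on blood counts and transfusion need. A patient with no target lesion cannot be a CT-based PR, because that rests on target-lesion SPD. The PET-CT column does have a marrow entry for PR ("Residual uptake higher than uptake in normal marrow but reduced compared with baseline"), so the gap is specific to CT. Entry without a lesion would be through Protocol 4.1.2 item 11b, whose only example is Sézary syndrome; its use in Cohort 5 is my inference.

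**2. How many patients?** The documents do not say. SAP Appendix B has 22 *Others* label lines: 4 ATLL, 2 T-PLL and 1 LGL among them. The firm conflict is ATLL plus LGL, 4 + 1 = 5 lines. These are labels, not patients.

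**3. What does one patient weigh?** I used the Clopper-Pearson interval named in SAP 7.8.1: lower limit = Beta(0.025; x, n-x+1), upper limit = Beta(0.975; x+1, n-x).

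- The plan's own figures reproduce: 1/20 has an upper limit of 24.9% (stated as about 25%), and 12/40 gives 30.0% (16.6 to 46.5), as in the protocol synopsis.
- Shift per reclassified patient: 1/20 = 5.0, 1/40 = 2.5, 1/50 = 2.0 points.
- Around 12/40: 11/40 = 27.5% (14.6 to 43.9); 13/40 = 32.5% (18.6 to 49.1).
- Closure rule: one reclassified patient among the first 20 separates 1/20 (close) from 2/20 (may expand).

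**4. What would a report with and without these patients look like?** This is an illustration on assumed numbers, 12 responders among 40. It shows the effect of leaving patients out, not of misclassifying them.

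| Patients left out (assumed) | Responders among them | ORR in the rest |
|---|---|---|
| 2 | 0 | 12/38 = 31.6% (17.5 to 48.7) |
| 2 | 2 | 10/38 = 26.3% (13.4 to 43.1) |
| 4 | 0 | 12/36 = 33.3% (18.6 to 51.0) |
| 4 | 1 | 11/36 = 30.6% (16.3 to 48.1) |
| 4 | 2 | 10/36 = 27.8% (14.2 to 45.2) |
| 7 | 0 | 12/33 = 36.4% (20.4 to 54.9) |
| 7 | 3 | 9/33 = 27.3% (13.3 to 45.5) |

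**The case against.** The strongest reply is that this may be wording only. Response is the investigator's call, the SAP describes no re-derivation from lesion data, and investigators worked under a protocol that schedules a leukemic response assessment. If they used Appendix 4, their calls go straight into ORR and the Lugano label is merely incomplete. This stands: an effect on results is not shown. The SAP would still misdescribe its primary endpoint.

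The protocol is also not uniform. Its synopsis, 3.1.5 and 11.1.3 carry no leukemic exception, and no document states which text prevails. That is fair, but 8.1 and Appendix 4 are the specific provisions. Sections 3.1.5 and 11.1.3 do not support the SAP either, since they cite the earlier IWG criteria and not Lugano.

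Section 8 attributes its changes to data limitations recorded in a Study Data Handling Document that is not available here. The matter may be explained there, but section 8 itself is silent.

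A reader might count the two T-PLL lines and call it 7 of 22. The protocol only encourages IWCLL for PLL, so Lugano there is not a departure; what is missing is a statement of which criteria were used. A reader might also dismiss LGL because Appendix B footnotes it as miscategorized. The footnote leaves LGL in the column, does not cover ATLL, and conflicts with Protocol 4.1.2 item 7 and 8.1, which list LGL as a leukemic form of PTCL.

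**Conclusion.** The SAP's rule for Cohort 5 response and PFS progression, as written, contradicts Protocol 8.1 and Appendix 4 for ATLL and LGL, and section 8 does not declare it. It should be fixed. The textual mismatch is certain; its effect on results is unknown.

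The weight is 2.5 points of Cohort 5 ORR per reclassified patient at n=40 (5.0 at n=20, 2.0 at n=50), and more in the smaller *Others* column. These cohort sizes come from the planned ranges, not from an observed Cohort 5 count.

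A reader might infer that the Cohort 5 ORR is biased, or inflated. The documents do not support that: differences can run both ways, patient numbers are not given, and which criteria investigators applied cannot be seen. Equally, the absence of a success criterion does not make the point empty, because the closure rule counts responses. The documents do not show whether that rule was ever close to its boundary in Cohort 5.

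**What to change.** 1. In SAP 7.8.1 and 7.8.2.4, state that Cohort 5 response is investigator-assessed under Protocol 8.1 and Appendix 4: Table A4-12 for ATLL, Table A4-13 for LGL, the criteria the investigator used for PLL, and Lugano for other PTCL. Make the matching change to the progression reference for PFS (7.8.2.1), and add one for DOR (7.8.2.2).
2. List the criteria used for each ATLL, PLL and LGL patient. Do the same for the aggressive epidermotropic CD8+ CTCL case that Appendix B footnotes as miscategorized, since Protocol 8.1 sends CTCL to mSWAT.
3. State how ATLL uncertified complete remission and LGL treatment failure map to best overall response, without overriding investigator calls. Table A4-13 has no stable or progressive category, so the mapping must also say what counts as clinical benefit and progression in LGL.
4. If the leukemic assessments were not recorded, declare Lugano-only in section 8. Then report Cohort 5 and *Others* ORR with and without ATLL, PLL, LGL and the miscategorized CTCL case.
5. Reconcile the Appendix B LGL footnote with Protocol 4.1.2 item 7 and 8.1.

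The cost is SAP wording, some mapping work and a per-patient listing. The price in interpretation is slightly mixed criteria within *Others*, which the listing makes visible.

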7.8.2. Secondary Efficacy Endpoint

7.8.2.1. Progression free survival

Progression-free survival (PFS) is defined as the time from the start of study treatment to the first documentation of disease progression as assessed by investigator (see appendix C) or death from any cause, whichever occurs first.

Progression-free survival = (first documentation of disease progression or death – first dose date of study treatment + 1) /30.4375 in months.

PFS will be right censored for subjects who meet one of the following conditions: 1) no baseline disease assessments; 2) starting a new anti-cancer therapy before documented disease progression or death; 3) progression or death immediately after more than 6 months since the last disease assessment (or more than 12 months if beyond cycle 12); and alive without documented disease progression. The censoring convention follows the FDA guidance for Industry Clinical Trial Endpoints for the Approval of Cancer Drugs and Biologics (2018) and references within the guidance document. The censoring rules are summarized in Table 1.

Table 1. Date of Event or Censoring for PFS

Scenario	Date of PFS Event or Censoring	Outcome
Death or progression between the planned disease assessments	Date of death or first disease assessment showing PD, whichever occurs first	Event
Death before the first disease assessment	Date of death	Event
No baseline disease assessment	Date of first dose of study treatment	Censored
New anti-cancer treatment started	Date of last disease assessment prior to or on the date of new anti-cancer treatment	Censored
Death or progression immediately after missing more than 1 scheduled disease assessment ^[1]	Date of the last disease assessment before death or progression	Censored
Alive without documented disease progression	Date of last disease assessment	Censored

^[1] missing ≥ 6 months if in Cycle 1~12 or missing ≥ 12 months if beyond Cycle 12

The distribution of PFS, including median and the PFS rate at selected time points (e.g. 12 months), will be estimated using the Kaplan-Meier method. The 95% CI for the median and the quartiles of PFS will be estimated using the Brookmeyer method (Brookmeyer 1982). The 95% CI for the PFS rate at the selected time points will be estimated using the Greenwood formula (Greenwood 1926). The duration of PFS follow-up will be estimated using the reverse Kaplan-Meier method (Schemper and Smith 1996). The Kaplan-Meier curve for PFS will be plotted for Cohort 1 and 2 FL patients, respectively.

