#### **7.3.2.1. Visit Reduction for Response Patients after Cycle 12**

If a patient experiences a treatment response while on study treatment, the patient may be eligible for a reduced visit schedule after Cycle 12 or at the discretion of the Sponsor. At the discretion of the Investigator based upon clinical judgement and with Medical Monitor approval, the patient’s visit cycle may be reduced from every cycle (e.g., C12D1, C13D1, C14D1) to every 3 cycles (C12D1, C15D1, C18D1), corresponding with the “Additional Tests Every 3 Cycles” schedule in [Appendix 1](#).

If a patient experiences a response and their visit reduction is approved by the Medical Monitor to every 3 cycles, the site will call the patient and conduct a telephone visit for every cycle when the patient is not on-site. During this call, site staff should obtain information about the patient’s overall health, any reportable adverse events, or other relevant clinical information that would normally be collected on-site.

In these cases, patients may be dispensed enough study drug and study materials (e.g., patient diaries) to accommodate the reduced visit frequency.

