**APPENDIX 1. SCHEDULE OF ASSESSMENTS – PHASE 2A (EXPLORATORY)**

PROCEDURES	Pre-Treatment	Phase 2A Treatment Period																		Follow-up		
	SCREENING	CYCLE 1										CYCLE 2				CYCLE 3 (and C6, C9, C12, C15, C18+)		CYCLES 4 & 5 (and C7, C8, C10, C11, C13, C14+)		30 Days Post-last Treatment		
		D1	D2	D8		D9	D15		D22 Cohort 2 Only		D1	D15		D1		D1						
	D -21	Pre-dose	Post-dose	Pre-dose	Pre-dose	Post-dose	Pre-dose	Pre-dose	Post-dose	Pre-dose	Post-dose	Pre-dose	Post-dose	Pre-dose	Post-dose	Pre-dose	Post-dose	Pre-dose	Post-dose			
Visit Windows (Days)	Within 21 Days Prior to C1D1	N/A		N/A		±1		N/A		±2		±2		±3		±2		±3		±3		±3
General/Safety Assessments																						
Obtain Informed Consent	X																					
Review Inclusion/Exclusion Criteria	X	X																				
Medical History and Prognostic Factors 	X	X																				
Physical Examination	X	X			X			X					X					X			X	
Height	X																					
Weight	X	X											X					X	X		X	
Vital Signs 	X	X	X		X	X		X	X	X	X	X		X			X	X	X		X	
12-Lead ECG	X																				X	
ECOG Performance Status	X	X												X				X			X	
Global Health Assessment 	X	X			X			X						X				X				
Concomitant Medications	X 	X 			X			X			X			X		X		X		X		
Adverse Events	X	X	X	X	X	X	X	X	X	X	X	X	X	X	X	X	X	X	X	X	X	
Cerdulatinib Administration 			X		X		X		X		X		X		X		X		X			
Rituximab Administration (Cohort 2 Only) 			X			X			X		X							X 		X 		
Local Disease Assessments and Laboratory Tests																						
Bone Marrow Biopsy and Aspirate 	X																	X		X		
CT or CT/PET 	X																	X				
Optional Lymph/Tumor Node Biopsy 		At any time throughout the study																				
Optional Tumor Block/Unstained Slides 	X																					
EBV PCR 	X																					
HIV/HBV/HCV infection testing 	X																					
Serum Chemistry and Hematology 	X	X			X			X					X		X			X		X	X	
Urinalysis (microscopic analysis as clinically indicated)	X	X											X					X		X	X	
Urine or Serum Pregnancy 	X	X											X					X		X	X	
PT/PTT/INR	X																				X	
Beta-2 Microglobulin, Lymphocyte Subsets, Immunoglobulin Levels 	X 	X			X			X					X					X				
CRP and ESR-Westergren (Sed. Rate)		X			X			X					X					X				

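### Beyond Cycle 12 the PFS/DOR missed-assessment rule allows a 12-month gap although scans stay every 3 cycles, so events after two or three missed scans are kept, contrary to the rule's own label

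*SAP*

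**What the plan says.** SAP 7.8.2.1 states the rule in three places.

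- **Table 1, row label:** "Death or progression immediately after missing more than 1 scheduled disease assessment". The outcome is censored at the last disease assessment before the event.
- **Table 1, footnote 1:** "missing ≥ 6 months if in Cycle 1~12 or missing ≥ 12 months if beyond Cycle 12".
- **Body text:** censoring applies to "progression or death immediately after more than 6 months since the last disease assessment (or more than 12 months if beyond cycle 12").

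A progression that is not censored takes the date on which it was seen; the entry is "Date of death or first disease assessment showing PD, whichever occurs first". SAP 7.8.2.2 carries everything over to DOR: "The censoring convention and analysis method of DOR will be the same as those for PFS in Section 7.8.2.1".

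The schedule comes from the protocol. In Appendix 1, CT or CT/PET sits in the column headed "CYCLE 3 (and C6, C9, C12, C15, C18" and onward. Section 7.3.3.1 sets the cycle at 28 days. Section 7.3.2.1 lets responders attend less often after Cycle 12: visits "may be reduced from every cycle (e.g., C12D1, C13D1, C14D1) to every 3 cycles (C12D1, C15D1, C18D1"). The visits that remain are the scan visits. The Synopsis ties PK sampling to tumour assessment every 3 cycles without an end, and Section 3.1.5 gives 8 to 12 weeks with no exception for late cycles.

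**The concern.** A missed-assessment rule is meant to separate events whose timing is reasonably known from those found after a long unobserved stretch. The row label sets the boundary at one missed scan. The time limits are supposed to express that boundary in months, which works only if the limit fits the scan interval. The limit doubles after Cycle 12; the scan interval does not. The same pattern of missed scans is then censored early in the trial and counted as an event later.

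Two smaller gaps make the rule hard to program consistently. The text requires the gap to exceed the limit, while the footnote includes equality. Nor is it stated whether the phrase about being beyond Cycle 12 refers to the last scan or to the event.

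What is at stake is the late part of the PFS and DOR curves in the three cohorts whose efficacy is summarised, and whether two programmers working from the same SAP would obtain the same curves.

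**Working it through.** **Inputs**
- Cycle length 28 days (Protocol 7.3.3.1); scans every 3 cycles (Appendix 1). Interval = 3 × 28 = 84 days. This is nominal, because dose interruptions past Day 28 delay the next cycle.
- Month length 30.4375 days, from the SAP formula "first dose date of study treatment + 1) /30.4375 in months".
- Limits: 6 × 30.4375 = 182.6 days; 12 × 30.4375 = 365.25 days.
- Windows: scans up to 7 days before the visit, visits ±3 days. Largest combined slack between two scans = 7 + 3 + 3 = 13 days.

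**Gap between the last scan and the detecting scan after k missed scans = (k + 1) × 84 days**

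| Missed | Gap (days) | Months | With ±13 days | 6-month limit | 12-month limit | Row label |
|---|---|---|---|---|---|---|
| 1 | 168 | 5.5 | 155–181 | event | event | event |
| 2 | 252 | 8.3 | 239–265 | censored | **event** | censored |
| 3 | 336 | 11.0 | 323–349 | censored | **event** | censored |
| 4 | 420 | 13.8 | 407–433 | censored | censored | censored |

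The 6-month limit reproduces the label on every line; the 12-month limit fails at two and three missed scans. The windows change no classification.

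**What interval would fit 12 months?** One missed scan must fall below the limit and two must reach it: 2 × I < 365.25 ≤ 3 × I, so I lies between about 122 and 183 days. The protocol sets no such interval. At the 56-day end of Section 3.1.5, up to five missed scans would still count as events (6 × 56 = 336 days).

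**Example.** Day 1 of cycle c is study day 28 × (c − 1) + 1. Last scan at C15D1 (day 393), next scan at C24D1 (day 645) shows progression, two missed. Under the 12-month limit this is an event at 645 / 30.4375 = 21.2 months. Under the row label it is censored at 393 / 30.4375 = 12.9 months. A progression that arose in the first missed interval is dated up to 252 − 84 = 168 days after the scan due to show it; with three missed, 336 − 84 = 252 days.

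**Ambiguity example.** Last scan C9D1 (day 225), progression at C18D1 (day 477), gap 252 days. If Cycle 12 is judged by the last scan, the 6-month limit applies and the patient is censored at 7.4 months. If it is judged by the event, the 12-month limit applies and the patient has an event at 15.7 months.

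**When the effect starts.** The first scheduled scan beyond Cycle 12 is C15D1, day 393 = 12.9 months. No progression found at a scheduled scan that the clause reclassifies can be dated before that.

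**Size, by illustration.** Assumed: exponential PFS with median 10 months, 20% or 40% of scans after Cycle 12 missed at random, 40,000 simulated patients. None of these inputs comes from the documents. SAP rule minus a 6-month rule at all cycles:
- 12 months: 0.00 points
- 18 months: about +0.3 to +1.1 points
- 24 months: about -0.7 to -2.6 points

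About 4% to 12% of patients are classified differently. At 24 months the assumed true PFS is 18.9%; one run gave 20.1% (SAP) against 20.8% (6-month) with 20% missed, and 21.4% against 23.9% with 40% missed.

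**The case against.** **The limits may be deliberate.** They are numeric and appear twice; the row label could be shorthand. SAP Section 8 attributes changes to data limitations recorded in a separate data handling document that is not available here. This leaves the intent unknown, but Section 8 does not list this rule among its changes and neither document gives a reason for doubling the limit. If the limit is intended, the label is wrong and still has to change.

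**Keeping observed events is defensible.** The row covers deaths, whose dates need no scan, and censoring after missed visits may be informative. In the illustration the 6-month rule is the further of the two from the assumed truth at 24 months. This stands as an argument for a sensitivity analysis. It does not rescue the text, because the SAP's own label already censors deaths and progressions after more than one missed assessment.

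**A flat 6-month limit has its own fault.** One missed scan plus a 28-day cycle delay gives 168 + 28 = 196 days, above 182.6, so a patient with a single missed scan would be censored. This stands and shapes the fix.

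**The reach is small.** Follow-up ends 30 days after treatment, so a progression found by scan after two or three missed scans essentially requires staying on drug while skipping consecutive scans. The cohorts are exploratory, at 20 to 50 patients, with no success criterion. This also stands.

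**Stronger readings that the documents do not support.** A reader might infer that late progressions are treated as if found on time; they are not, since Table 1 dates them at the late scan. A reader might infer that the rule flatters durability; the sign reverses between 18 and 24 months, because late dating raises the curve while retaining the event lowers it later. A reader might also infer that the 12-month PFS rate is distorted, because Cycle 12 ends at about 11.0 months (336 days); reclassified scan-detected progressions begin at 12.9 months.

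**Conclusion.** Wrong as written. Beyond Cycle 12 the operative limit contradicts the rule that it is meant to define: it keeps events after two and three missed scans and censors only from four. This follows from the documents' own figures and holds under the visit windows. It rests on the nominal 84-day interval, and no passage sets a longer one.

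The consequence is limited. It concerns secondary PFS and DOR in FL Cohorts 1 and 2 and PTCL Cohort 5, for patients still followed after about 12.9 months on treatment. ORR is not affected, nor is the 12-month PFS rate in the scenario examined, where all scans up to C12D1 are done and events are found at scheduled scans. The direction is not fixed, and the sizes of up to about 1 point at 18 months and 2.6 points at 24 months depend on the assumed median and on 20–40% of late scans being missed. With fewer missed scans the effect would shrink.

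**What to change.** Use one rule at all cycles in the text, Table 1 and the footnote, defined by the number of missed scans: censor at the last adequate assessment when two or more consecutive scheduled assessments were missed immediately before the progression or death. Count them against the patient's actual cycle schedule, allowing for visit windows and cycle delays; about 6 months can be given as the nominal equivalent but should not be the test. Delete the 12-month clause. That also removes the mismatch over equality and the question of what lies beyond Cycle 12. State that DOR follows the same rule.

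Add a sensitivity analysis for PFS and DOR that counts every documented progression and death as an event whatever the gap.

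Cost: one SAP sentence with its table row and footnote, one program parameter replaced by a count of missed scans, and one extra set of estimates. The downside is that a few late events become censored, which the sensitivity analysis makes visible.
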